Delirium occurrence rates for hospitalized older adults range from 29-64%. Although 30-50% of delirium is preventable, it frequently goes unrecognized until acute and potentially devastating. The Hospital Elder Life Program (HELP) is a multidimensional clinical strategy that is effective in preventing delirium, but labor intensive. This randomized controlled study will test an innovative method to implement the HELP approach: a tablet-based digital avatar that can see, hear, and talk with a patient using speech-to-text technology. The avatar platform has already been validated at Jamaica Hospital in a previous study in 2016: “GeriJoy: The Use of an Avatar Virtual Service Animal to Improve Outcomes in Hospitalized Older Adults” as well as in multiple published studies to effectively provide psychosocial support to older adults across varied clinical settings. This study will focus on discerning the relative impact of implementing HELP through this technology. Participants aged 65+ will be randomly assigned to receive one of the following interventions in addition to usual care throughout their hospitalization: 1) an avatar delivering HELP protocols and socialization; or 2) no intervention beyond usual care. Participants will be assessed by the investigators upon admission to the study and reassessed upon 24-hour discharge notification using the Short Portable Mental Status Questionnaire (SPMSQ), Memorial Delirium Assessment Scale, and Short CAM (Confusion Assessment Method). Based on patient medical records of sedation, restraints and incidence of falls and delirium, pre- and post-assessment scores will be compared using paired t-tests to determine outcomes among the groups. If the avatar is effective in improving outcomes by providing HELP interventions, the number of patients who benefit from HELP could increase greatly due to technology-enabled cost efficiencies, and protocol and data collection standardization across many sites.

Specific aims/hypotheses

For hospitalized older adults, will the use of an avatar delivering HELP protocols...

1. decrease delirium incidence and severity,
2. decrease falls and falls with injury,

..more than usual care?

Background and significance

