Study design: This randomized controlled trial will compare outcomes on delirium, falls, sitter utilization (1:1's) and restraints between the two study groups: HELP-protocolized avatars, and usual care. Each day of the study, enrollment of subjects will proceed with randomization of each subject between groups (the randomization primarily effects delirium data, which is assessed by subject) until there are no more available intervention devices. However, falls and other unit-level grouping are non-randomized (see below).

Sample Size: A total of 3,650 patients (avatar and usual care) are expected to be enrolled at JHMC over the course of two years, based on an estimated average length of stay of 4 days.

Study Units: Patients will be recruited from the following units at JHMC: 3S, 3N, 4S, IMCU, 5N, 6S, and Hospice. Because the hospital only collects/reports unit-by-unit quarterly falls data, we will take the following measures to ensure that falls data collected for study purposes are a valid indicator of possible intervention effect:

- There are expected to be protocol and technical adaptations made during the first quarter of the study, and the study will not begin enrolling subjects exactly at the start of a calendar quarter. Therefore, the first calendar quarter of falls data is not intended to provide useful data regarding unit-level falls outcomes, and enrollment of patients may be performed on select units by convenience.
- Starting on the first day of the first full calendar quarter, a unit-equitable enrollment protocol will be implemented in which one or more of the study units at any time may be formally designated for active subject enrollment, and such designated study units will have their enrollment numbers monitored and rounding adjusted as needed to ensure that, on average, each designated unit receives a similar number of intervention patients at any time. Which units are designated or not designated for enrollment may be changed at the start of each calendar quarter to compare the effect of the intervention and to control for annual changes in fall rates. Research assistants will not enroll any patients on units not designated for enrollment, but will continue to round currently enrolled patients until they are dis-enrolled.

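### Aim 2 sets falls on avatar against usual care, but Study Units takes falls from quarterly unit totals that cannot be split by randomised arm, and no analysis of fall counts is given

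*Combined protocol and SAP*

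**What the plan says.** Under Specific aims/hypotheses, the second aim is to "decrease falls and falls with injury" more than usual care does. Study design opens in the same terms: "This randomized controlled trial will compare outcomes on delirium, falls, sitter utilization" use and restraints between the two study groups. It then randomises each subject individually, says that this mainly serves the delirium data, and adds that "falls and other unit-level grouping are non-randomized (see below").

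Study Units gives the reason, "Because the hospital only collects/reports unit-by-unit quarterly falls data", and lists measures meant to ensure that the falls data are "a valid indicator of possible intervention effect":

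- The start-up period is set aside: "the first calendar quarter of falls data is not intended to provide useful data regarding unit-level falls outcomes".
- Enrolment is monitored so that, on average, "each designated unit receives a similar number of intervention patients at any time".
- The units open to enrolment may be changed at the start of each quarter. One or more units may be designated at any time.

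Statistical analyses specifies paired t-tests of pre- and post-assessment scores, and nothing for fall counts or rates. The opening summary points to another source for falls: "Based on patient medical records of sedation, restraints and incidence of falls and delirium".

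**The concern.** Both randomised arms and non-enrolled patients lie in the same units. A unit's quarterly fall total therefore carries no arm label, and the comparison that Aim 2 names cannot be formed from it. What is left is a comparison of designated with undesignated units or quarters. That comparison is not randomised, has no stated rule for choosing units, and has no guaranteed comparator.

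Falls are one of only two stated aims. If the trial runs as Study Units describes, a null unit-level result could be dilution, and a positive or negative one could reflect which units were opened to enrolment. Neither would answer whether the avatar reduces falls more than usual care.

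**Working it through.** **The safeguards, one by one.**

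- Setting aside the first quarter removes start-up noise. It does not attach an arm to any fall.
- Balancing equalises the number of avatar patients per designated unit, not their share of the unit's patients. It also reduces the exposure contrast among designated units.
- Changing designation is optional. No random or fixed rule is given, and nothing requires any unit to stay undesignated.

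**Inputs from the plan.** 3,650 patients in both groups together, two years and a mean stay of 4 days (Sample Size); seven units (Study Units); significance at 0.05 (Statistical analyses). The 3,650 is a throughput figure: 20 patients at once × 730 days / 4 days = 3,650. The 20 is inferred, not stated, and no fall rate or effect size enters the figure.

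**Assumptions, because the plan is silent.** 1:1 allocation, so 10 avatars in use at once ((3,650/2) × 4 / 730); 30 to 40 beds per unit at 90% occupancy; 7 full quarters of 91.25 days; 3 to 5 falls per 1,000 patient-days; equal fall risk in enrolled and other patients; no spill-over; Poisson counts without between-unit variation; the same units designated throughout; a two-sided test.

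**Dilution.** Unit rate ratio = 1 − 0.5 × 10 / (units × beds × 0.9), for a true rate ratio of 0.5 among avatar patients. Power = Φ(z − 1.96) + Φ(−z − 1.96), with z = |ln RR| / √(1/d₁ + 1/d₀), where d₁ and d₀ are expected falls in the designated and the remaining units.

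| Designated units | Beds per unit | Enrolled share of occupied beds | Unit rate ratio | Power at 3 / 5 falls per 1,000 |
|---|---|---|---|---|
| 1 | 30 | 20/27 = 74% | 1 − 5/27 = 0.81 | 24% / 36% |
| 1 | 40 | 20/36 = 56% | 1 − 5/36 = 0.86 | 19% / 28% |
| 3 | 30 | 20/81 = 25% | 1 − 5/81 = 0.94 | 9% / 12% |
| 3 | 40 | 20/108 = 19% | 1 − 5/108 = 0.95 | 8% / 10% |

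The one-unit case is demanding, since more than half of that unit's occupied beds would hold enrolled patients.

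**Sensitivities.**

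- 2:1 allocation (13.3 avatars), one unit of 30 beds: 1 − 0.5 × 13.33/27 = 0.75.
- Spill-over cutting other patients' falls by 10%, three units: (10 × 0.5 + 71 × 0.9)/81 = 0.85 with 30 beds; (10 × 0.5 + 98 × 0.9)/108 = 0.86 with 40.
- Baseline rate 10% lower or higher in three designated 30-bed units: 0.938 × 0.9 = 0.84; 0.938 × 1.1 = 1.03.
- Baseline excess that cancels the effect entirely, three units: 1/0.938 − 1 = 6.6% (30 beds); 1/0.954 − 1 = 4.9% (40 beds).

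**Comparison by randomised arm.** Patient-days per arm = 1,825 × 4 = 7,300.

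| Usual-care rate per 1,000 | Expected falls at RR 0.5 | 95% interval around 0.5 | Power, RR 0.5 | Power, RR 0.7 |
|---|---|---|---|---|
| 3 | 21.9 v 10.95 | 0.24 to 1.03 | 47% | 19% |
| 5 | 36.5 v 18.25 | 0.29 to 0.88 | 68% | 28% |

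Without the first quarter (7/8 × 7,300 = 6,387.5 patient-days per arm), power is 42% to 62% for RR 0.5 and 17% to 25% for RR 0.7.

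**The case against.** The plan is open about this. It says in the same paragraph that falls are not randomised and gives the practical reason, and Aim 2 says only more than usual care, without mentioning randomised arms. The permission to change designation each quarter describes a quasi-experiment over units and time. If designation did rotate, units could act as their own controls, and stable baseline differences would largely drop out once unit effects were fitted. The baseline-difference figures above describe a static, unadjusted analysis that the plan does not specify. The consequence also depends on Study Units being the operative source. If falls come from patient records, as the opening summary says, an arm comparison is possible. Background and significance reports fewer falls among avatar patients in the 2016 study at the same hospital, without saying how falls were captured.

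Much of this is fair. The numbers are illustrations, and a well-run rotation would limit one bias. But rotation is only permitted, with no rule, no assured comparator and no model with unit effects. Disclosure leaves Aim 2 and the opening of Study design unchanged. The plan also goes beyond disclosure when it says its measures ensure a valid indicator. The conflict over the source is part of the defect, and either resolution requires a change of text.

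**Conclusion.** The concern holds, and the plan must be changed on this point. With falls taken from unit reports, Aim 2 cannot be answered by the randomised comparison, and whichever source is used, no analysis of falls is specified. This conclusion rests on the plan's own text and not on the assumed inputs.

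Under those inputs, an effect confined to avatar patients shrinks from 0.5 to between 0.81 and 0.95 at unit level, with power of 8% to 36%. Overdispersion or between-unit variation would lower that power further. Dilution pulls towards no difference, but with spill-over or selective designation the net bias has no known direction.

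**What to change.** 1. Reconcile the opening summary and Study Units on where falls data come from.
2. Record falls and injurious falls, with dates, for every enrolled patient from the medical record and at the existing daily round.
3. Make the Aim 2 analysis falls per patient-day by randomised arm (Poisson or negative binomial, adjusted for unit), by intention to treat through discharge. Use chart review for subjects unenrolled because of 1:1, so that they still count in their arm.
4. Keep the quarterly unit data as secondary.
5. If patient-level capture proves impossible, restate Aim 2 as an exploratory, non-randomised unit-level comparison. Fix or randomise the designation schedule in advance, keep some units undesignated each quarter, and specify a count model with unit and quarter effects.

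The cost is one item on the daily round form plus chart abstraction for up to 3,650 patients. It is less if the data and safety monitoring plan, which is referred to but not reproduced, already records their falls.

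There are downsides. The patient-level estimate is imprecise, as the second table shows, and injurious falls will be rarer still. Spill-over to usual-care patients on the same unit would make the arm comparison understate the effect. Avatar patients are watched by camera, so their falls may be noticed more fully; relying on charted falls limits this. The fallback costs only text and a schedule, but gives up the randomised falls question.

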Sample inclusion and exclusion criteria: All patients over age 65 on the pilot units who can provide informed consent or who have a proxy who can provide informed consent will be assessed by the investigators. Those who consent will be randomly assigned to one of the two treatment conditions unless they meet any of the exclusion criteria: a.) aggression or combativeness with intent to harm self or others, b.) alcohol or drug withdrawal, c.) severe hearing impairment and simultaneous severe vision impairment, despite assistive devices, d.) cannot verbalize fluently in either Spanish or English, e). on 1:1;if a study subject is put on 1:1 during the duration of the study, he/she will be unenrolled from the study, f) expected to be discharged within the next 24 hours.

Instruments

Pre- and post-intervention:

1. Short Portable Mental Status Questionnaire
2. Short CAM (Confusion Assessment Method) – also conducted during each daily round
3. Memorial Delirium Assessment Scale – if CAM screens positive

Statistical analyses: Demographic variables including age, gender, education, race/ethnicity, and living arrangements will be collected to determine equivalency of study groups. Pre-and post-assessment scores will be compared using paired t-tests to compare means at baseline and at hospital discharge within each group, and between groups. All data will be analyzed using the Statistical Package for Social Sciences software (SPSS, Inc. Chicago, IL). Statistical significance will be defined as $p \leq 0.05$.

Additional Information

Photos of Avatar

Figure D.8.1: A hospitalized older adult in South Carolina enjoys the company of an avatar as it plays music and shows a photo. A “fisheye lens” mounted to the top of the avatar device enables wide-angle visual monitoring, to enable appropriate reaction by the avatar to not only the patient’s facial and body language cues, but also any dangerous unassisted transfers, tugging on IV lines, etc. To help with re-orientation, the window behind the avatar reflects the actual weather report, and the lighting of the avatar’s environment reflects day or night status. A video showing the patient talking to the avatar and singing along is available at <https://www.youtube.com/watch?v=WfWjazOmKUk>

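### Only avatar numbers are balanced across designated units, and unit is absent from the delirium analysis, so a little precision is lost (minor)

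*Combined protocol and SAP*

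**What the plan says.** The combined protocol and SAP recruits from seven units: "3S, 3N, 4S, IMCU, 5N, 6S, and Hospice" (Study Units). Under Study design, "enrollment of subjects will proceed with randomization of each subject between groups", and this continues "until there are no more available intervention devices". Eligible, consenting patients are "randomly assigned to one of the two treatment conditions" (Sample inclusion and exclusion criteria). No ratio, blocking, strata or concealment method is described.

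Study design says that randomisation mainly serves the delirium data, and that "falls and other unit-level grouping are non-randomized". The Study Units section then sets out measures meant to make the quarterly falls data by unit usable. In the first, partial quarter, "enrollment of patients may be performed on select units by convenience". From the first full quarter, "one or more of the study units at any time may be formally designated for active subject enrollment", enrolment numbers on those units are monitored, and "rounding adjusted as needed to ensure that, on average, each designated unit receives a similar number of intervention patients at any time".

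The Statistical analyses section plans paired t-tests of pre- and post-assessment scores, within and between groups. The baseline variables listed there are demographic; unit is not among them.

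**The concern.** The rounding rule controls the number of avatar patients on each designated unit and says nothing about usual-care patients. If randomisation is not stratified by unit, the number of usual-care patients per unit is whatever chance gives. Unit is known for every patient before assignment, and staff already track enrolment by it. The names IMCU and Hospice suggest that delirium risk may differ between some units. If it does, part of the variation in the delirium outcome lies between units. Leaving unit out of both the described randomisation and the analysis keeps that part as noise in the comparison that randomisation is meant to protect. What is at stake is precision on the first aim, delirium incidence and severity.

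**Working it through.** **The plan's own figure.** Sample Size expects 3,650 patients over two years with a 4-day average stay. One place turns over 730 / 4 = 182.5 times, so 3,650 / 182.5 = 20 patients enrolled at once. The number of places is not stated, so the figure is reproduced only if 20 is assumed. It is a throughput figure; no power calculation is given.

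**Inputs.** N = 3,650 (Sample Size). Seven units (Study Units). Assumed: equal unit sizes, 1:1 allocation, a yes/no delirium outcome, and unit rates spread over 29–64%. That range is given in the opening summary for hospitalised older adults in general, not for these units.

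**Formulas.** Let p̄ be the mean of the unit rates and V their variance.
- Share of outcome variance between units = V / [p̄(1 − p̄)]
- SE of the arm difference ignoring unit = √[4 p̄(1 − p̄) / N]
- SE using unit = √{4 [p̄(1 − p̄) − V] / N}
- Ratio of the two = 1 / √(1 − share)

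For an even spread over 29–64%: p̄ = 0.465, p̄(1 − p̄) = 0.2488, V = 0.0136, share = 5.5%. SE = √(4 × 0.2488 / 3,650) = 1.65 points ignoring unit, and √(4 × 0.2352 / 3,650) = 1.61 points using it.

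| Assumed unit rates | p̄ | Share | SE ignoring unit (points) | SE using unit (points) | Ratio |
|---|---|---|---|---|---|
| Even spread, 29–64% | 46.5% | 5.5% | 1.65 | 1.61 | 1.03 |
| Six at 29%, one at 64% | 34% | 6.7% | 1.57 | 1.51 | 1.04 |
| Five at 29%, two at 64% | 39% | 10.5% | 1.61 | 1.53 | 1.06 |
| Three at 29%, four at 64% | 49% | 12.0% | 1.65 | 1.55 | 1.07 |
| Narrower: five at 29%, one at 40%, one at 50% | 33.6% | 2.7% | 1.56 | 1.54 | 1.01 |
| Wider: even spread, 10–80% | 45% | 22.0% | 1.65 | 1.45 | 1.13 |

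**Simulation of the rule.** 4,000 trials per setting, no treatment effect, N = 3,650, seven open units. Average lowest and highest unit counts:

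| Method | Avatar per unit | Usual care per unit |
|---|---|---|
| Simple randomisation, no steering | 239–283 | 239–283 |
| Rounds steered to the unit with fewest avatars | 260–261 | 230–292 |
| Blocks of 4 within unit | 259–262 | 259–262 |

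Steering moves the imbalance into the usual-care arm. The SD of the arm difference caused by unit mix alone is much the same with steering as without: 0.39 against 0.38 points (even spread), and 0.53 against 0.52 (two units at 64%). Mean bias with steering was 0.04 and 0.01 points, which is Monte Carlo noise.

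**Which remedy does the work.** SD of the estimated difference, even spread and two units at 64% respectively:
- steered, unit ignored: 1.65 and 1.60 points
- steered, unit used in the analysis: 1.60 and 1.51 points
- stratified randomisation: 1.60 and 1.54 points

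The Monte Carlo error of each SD is about 1.6 / √8,000 = 0.02, so the last two lines do not differ materially. Adjustment alone recovers essentially all the loss.

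**Smaller data sets.** At one quarter's share, 3,650 / 8 ≈ 456 patients, the unit-mix SD is 1.1–1.5 points and the SE ratio is again 1.03–1.06.

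**The case against.** The strongest objection is that this hardly matters. At 1,825 per arm, power for a 20% relative reduction is about 98% or more for usual-care rates of 29–64%, and 3,650 is not a powered target that the loss would erode. This stands, and it is why the point is minor.

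Second, the rounding rule was written for the falls data, which the hospital reports only by unit and quarter. It aims at similar numbers of avatar patients at the same time, and equal enrolment totals per unit would not guarantee that if stays differ. This stands too: the rule should not be replaced, and the simulation shows that it does not itself cost the delirium comparison precision.

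Third, the planned analysis is of pre- and post-assessment scores. A change from baseline already removes stable differences in level between units, so the gain for scores may be smaller than the table shows. This stands in part. Delirium incidence is also an aim, and a CAM-based yes/no outcome is where the calculation applies most directly.

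A reader might also infer three stronger things that the documents do not support:
- **That randomisation is declared unstratified.** The documents do not describe the method; that is silence.
- **That avatar numbers are balanced across seven very different units.** Balance applies to the designated units, which may be as few as one, and not in the first partial quarter. No case mix or delirium rate is given for any unit; the contrast rests on unit names.
- **That steering by staff who can see allocations biases the delirium result.** Steering chooses where to recruit before each patient is individually randomised. With concealed allocation and a constant ratio it produces chance imbalance only. A ratio that drifted by unit or quarter could make unit a confounder, but the documents describe no such drift.

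**Conclusion.** The point holds as a minor loss of precision. One arm's unit distribution is controlled, the other's is not, and unit is in neither the described randomisation nor the analysis. The standard error of the delirium difference is about 3–7% too large if unit rates span 29–64%, about 1% under a milder spread of 29–50%, and 13% under a spread of 10–80%. In absolute terms, within 29–64%, that is roughly 0.04 to 0.10 points on an SE of about 1.6. These figures assume unit rates that the documents do not give, equal unit sizes, 1:1 allocation and a yes/no outcome. The conclusion that no bias arises depends on concealment and a constant ratio, so the plan should state both.

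**What to change.** **Main change.** In Statistical analyses, specify the between-arm delirium comparison with unit at enrolment as a factor: Mantel-Haenszel across units for CAM yes/no, and a model with a unit term for the scores. A paired t-test cannot carry a unit term, so the comparison has to be written in one of these forms. The cost is one recorded variable, already monitored for enrolment, and six degrees of freedom. No extra patients or staff are needed.

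**State in Study design.** Give the randomisation method, the allocation ratio and how allocation is concealed.

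**Optional addition.** Stratify the concealed randomisation by unit, using randomly varying block sizes. The cost is one list per unit, and assignments become somewhat more predictable in an open-label trial. If this is done, unit should still be in the analysis; stratifying without adjusting leaves the reported SE too large.

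**Leave in place.** Keep the rounding rule for the unit-level falls data.

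### The units active each quarter are chosen without a rule and no falls contrast is named, so the falls comparison is open to bias whose size and direction depend on the analysis chosen later

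*Combined protocol and SAP*

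**What the plan says.** Specific aims/hypotheses lists falls, and falls with injury, as the second aim. Study design states that "falls and other unit-level grouping are non-randomized", in contrast to delirium, which is assessed on individually randomized subjects.

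Study Units gives the reason, "Because the hospital only collects/reports unit-by-unit quarterly falls data", and then lists measures meant to "ensure that falls data collected for study purposes are a valid indicator of possible intervention effect". The measures are:

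- The first, partial calendar quarter is set aside for falls.
- From the first full quarter, "one or more of the study units at any time may be formally designated for active subject enrollment". The units are "3S, 3N, 4S, IMCU, 5N, 6S, and Hospice", seven in all.
- Designated units are kept to similar average numbers of intervention patients.
- "Which units are designated or not designated for enrollment may be changed at the start of each calendar quarter", with the purpose "to compare the effect of the intervention and to control for annual changes in fall rates".

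The section does not say who designates units, how many are on at once, in what order, or whether the person deciding has seen fall counts. Statistical analyses describes paired t-tests on assessment scores. It gives no comparator, baseline period or model for falls.

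**The concern.** Two gaps combine. The choice of active units is free and can be revised on the same quarterly cycle as the falls reports, and the contrast that will be read as the falls result is not named.

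A unit with many falls in one quarter tends to have fewer in the next, with or without an intervention. If recently bad units tend to be switched on, a comparison with the preceding quarter credits that rebound to the avatar. If instead designated and other units are compared in the same quarter, the designated group holds more of the units with persistently high rates, and the avatar looks harmful.

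The two listed safeguards do not close this. Balancing intervention numbers works among units already designated and says nothing about which are chosen. Rotation can separate season from intervention only if its order is unrelated to recent falls, and the text does not require that. At stake is whether any falls result, in either direction, can be read as an effect of the intervention.

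**Working it through.** **The plan's own figure.** There is none for falls: no rate, effect size, power or number of unit-quarters. The one sample-size figure, 3,650 patients, is an enrolment forecast. It equals 730 days / 4-day stay × 20 patients enrolled at once, but the 20 is back-solved and not stated. It has no bearing on falls.

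**Inputs from the protocol.** There are 7 units, with quarterly counts by unit. Two years is 2 × 4 = 8 quarters, and setting the first aside leaves about 7.

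**Assumptions (not in the documents).** Mean falls per unit-quarter 4-10; between-unit CV of true rates 0-0.4; the 3 units with the highest last-quarter count are designated; no treatment effect; true unit rates constant over time.

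**Model.** Unit rates are gamma with the stated mean and CV, and quarterly counts are Poisson. Let A and B be the mean counts of designated units in the selection quarter and the next, and C and D the same for the other units.

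- Before/after change in designated units: B/A − 1
- Ratio of changes: (B/A)/(D/C) − 1
- Concurrent comparison: B/D − 1

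**One case in full (mean 6, CV 0.2).** Simulated means are A = 8.25, B = 6.44, C = 4.32, D = 5.67.

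- B/A − 1 = 6.44/8.25 − 1 = −22%
- D/C − 1 = 5.67/4.32 − 1 = +31%
- Ratio of changes = 0.781/1.313 − 1, about −40%
- B/D − 1 = 6.44/5.67 − 1, about +13% to +14%

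**Across the assumed range:**

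| Mean, CV | Before/after, designated | Ratio of changes | Concurrent |
|---|---|---|---|
| 4, 0 | −29% | −51% | 0% |
| 6, 0.2 | −22% | −40% | +13% |
| 10, 0.4 | −11% | −25% | +56% |

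**Seven quarters.** The same worst-3 rule was repeated each quarter for seven quarters. Counts were analysed by a linear model with unit and quarter effects. The spurious effect is about −7% to −10% of the mean rate (about −9% at mean 6, CV 0.2).

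**Weaker selection (mean 6, CV 0.2).** Suppose designation takes the top 3 units on a score that correlates only 0.3 with last quarter's count. The before/after change is −8% and the ratio of changes −14.5%. At correlation 0.5 these are −13% and −23%.

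**No selection.** With units drawn at random, every contrast is within about 0.1% of zero.

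**Wider grid (means 3-20; 1, 3 or 4 units on).** The before/after drop runs from 45% (mean 3, CV 0, 1 unit) to 5% (mean 20, CV 0.4, 4 units). False findings of a drop, nominally 2.5%, occur in 5-13% of before/after tests and 4-22% of tests on the ratio of changes. Under random designation they stay at or below nominal, within simulation error.

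**The case against.** The protocol says openly that the falls grouping is not randomized, sets aside the first partial quarter, and gives a purpose for changing designations that has nothing to do with picking bad units. It does not say that high-fall units will be chosen, that those choosing see the reports, or that last quarter's report is ready on the first day of the next. All of this stands.

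A reader might infer that the falls result will show a large false benefit, of the order of 40%, from regression to the mean alone. The documents do not support that. The figure needs strict selection of the worst three units on one quarter's counts and an analysis that uses that same quarter as the only baseline, and the plan specifies neither. Using all seven quarters with unit and quarter effects cuts the bias to about 7-10%, and comparing designated with other units in the same quarter reverses its sign. A reader might also infer that investigators intend to choose on falls; nothing in the text says so.

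The objection does not supply a rule. Admitting that a grouping is not randomized does not make it a valid indicator, which is what Study Units claims for it.

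**Conclusion.** The concern holds as a conditional one. The plan leaves the active units to discretion each quarter and names no falls contrast, so it does not deliver the validity it claims for the falls aim.

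If designation follows recent fall counts, then under the stated assumptions the bias is a spurious drop of about 11-29% in a one-quarter before/after comparison (25-51% as a ratio of changes), about 7-10% in a seven-quarter analysis with unit and quarter effects, and 0% to +56% against the avatar in a concurrent comparison. If designation is unrelated to past counts, the expected regression-to-the-mean bias is nil. Fall counts, between-unit variation and the strength of selection are all assumed, because the documents give none of them. Neither the size nor the direction of bias in this trial can be stated. The individually randomized delirium comparison is not affected by this point.

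**What to change.** Before the first full calendar quarter:

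1. Draw by computer, and lock, the on/off schedule of the seven units for all remaining full quarters (about 7). Let device capacity set the number of active units per quarter, since the protocol allows one or more and devices are limited. Give each unit both on and off quarters. Allow no change in response to fall counts.
2. Prespecify the falls analysis: unit-quarter fall counts in a Poisson or negative binomial model, with unit and quarter effects and unit patient-days as offset.

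The cost is one randomization list, a paragraph in the analysis plan, and collection of patient-days by unit and quarter if not already to hand. No extra patients or devices are needed. The real downside is that investigators lose discretion over which units are active.

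If that discretion must stay, record at each change the reason and the falls data seen, and report falls as exploratory rather than as a valid indicator of effect.
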